##### **6.5.8.2 Microbiological Cultures and Endotoxin – Product Water and Water from Holding Bag**

Samples of AMIA APD Solution Generation System water (product water) will be collected from the system by Baxter personnel or designees at installation at the patients' homes and at timepoints designated in the protocol (Study Treatment Weeks 1 [Study Visit 1], 4 [Study Visit 2], 8 [Study Visit 3] and 12 [Study Visit 4]). Product water from

---

the WD (pre-sterilizing filters) will be collected and tested for microbiological (including endotoxin) contamination per USP <61> and USP <85>.

Patients will generate water in the holding bag using the AMIA APD Solution Generation System during a simulated treatment in their home at timepoints designated in the protocol (Study Treatment Weeks 1 [Study Visit 1], 4 [Study Visit 2], 8 [Study Visit 3] and 12 [Study Visit 4]). Water in the holding bag will be collected and tested for microbiological contamination and endotoxin levels per USP <71> and USP <85>. Water in the holding bag (post-sterilizing filters) shall not exceed 0 CFU/mL for bacteria (no growth) and shall be < 0.03 EU/mL for endotoxins, consistent with Dianeal specifications for sterility.

All samples will be collected and packaged using aseptic techniques and sent to the central lab for analysis. Patients cannot treat on the AMIA APD Solution Generation System in the home until the post-installation product water results are received and reviewed by the study site and Sponsor per the AMIA APD Solution Generation System Patient Guide.

#### **6.5.8.3 Dialysate Composition Testing**

Patients will generate dialysis solution using the AMIA APD Solution Generation System during a simulated treatment in their home at timepoints designated in the protocol (Study Treatment Weeks 1 [Study Visit 1], 4 [Study Visit 2], 8 [Study Visit 3] and 12 [Study Visit 4]). The heater bag containing the dialysis solution generated by the simulated treatment will be collected by Baxter personnel or designee and shipped to a central laboratory for analysis of chemical composition.

#### **6.5.8.4 Additional Sampling Procedures**

The dual in-line sterilizing grade filters will be collected during sample collection procedures at each simulated treatment. The filters will be returned to Baxter R&D for possible investigation and used as an investigatory tool in the event of a positive finding from endotoxin or microbiological contamination in the holding bag.

#### **6.5.8.5 Process for Responding to Out-of-Specification Results**

##### **6.5.8.5.1 Decision Trees**

Clinical study decision trees for feed water, product water (pre-sterilizing filters), water from the holding bag (post-sterilizing filters), and dialysis solution samples have been developed and will be included in training materials and provided to study sites. These decision trees provide guidance to the clinical site and the Baxter team on

---

appropriate actions to be taken in situations where out of specification (OOS) results are received from the samples. Decision trees are structured to ensure patient safety. If test results are out of specification, the decision trees provide a mechanism for removing affected patient(s) from therapy if any safety concerns arise as determined by a clinician and/or the study team.

Upon confirmation of an OOS value for endotoxin or bacteria, a root cause investigation will be initiated, specific components of the AMIA APD Solution Generation System may be changed, and the replaced components may be sent to Baxter for functional assessment.

Additional actions may include:

- Resample.
- All device logs evaluated for anomalies.
- Aseptic procedure checklists recorded during sample collection and processing reviewed for anomalies.
- The Contract Laboratory will conduct an independent investigation of their procedures and processes for any OOS endotoxin or micro-organism result.

Consideration for additional actions such as retrieval and analysis of hardware and/or disposables, on site investigation for additional machine and environmental cultures.

#### **6.5.8.6 Chlorine and Conductivity Testing**

Chlorine testing of the water will be performed prior to each dialysis treatment. Water for chlorine testing is collected from the Water Sample Outlet and tested as specified in the AMIA APD Solution Generation System Patient Guide. Stricter local regulations for testing will be utilized if required.

Conductivity testing of the dialysate is performed by the AMIA APD Solution Generation System after each heater bag replenish prior to delivering fluid from that replenish to the patient without input from the user. If the conductivity test shows the dialysate is not within specification, the AMIA Solution Generation System will empty the heater bag and perform a new replenish. The system will warn the user if a conductivity issue is noted and user action is required.

Chlorine and conductivity testing are conducted as part of normal operation of the system to ensure device reliability. These results are captured in device logs and are not included

---

in study endpoints or any planned statistical analysis. Independent chlorine testing is included in the monthly product water testing and compliance of the conductivity of the solution is monitored through the heater bag dialysis solution testing.

### **6.6 Power Outage**

If the WD is off due to a power outage for more than 3 consecutive days during the use of the AMIA APD Solution Generation System, Baxter Technical Services must restore the WD to operating conditions before the patient can use the AMIA APD Solution Generation System for treatment. When not in use, the WD must be plugged in and turned on. The water supply to the WD and the patient's home must remain on and connected to the drain.

### **6.7 Boil Water Advisory Procedure**

If a municipal water supplier issues a "boil water advisory" for the feed water at a patient's location, the patient should discontinue use of the study generated PD solution and commence APD therapy using approved Dianeal Low Calcium (2.5 mEq/L) PD Solution bags or prior solution as assessed by the Investigator. Patients will be discontinued from the study following a boil water advisory affecting the feed water in their home.

### **6.8 Removal of Patients from the Study**

Patients are considered withdrawn / prematurely discontinued from the study if their participation is stopped before completion of the required evaluations as described in this protocol (see Section 3.5.1). If a patient is prematurely removed from the study, all data prior to discontinuation should be recorded in the eCRF and all available data will be included in all analyses.

The Investigator may terminate a patient's study participation at any time during the study if he/ she judges it to be in the patient's best interest. If a patient is withdrawn from the study, the Clinical Study Manager or Monitors should be informed at the earliest possible opportunity, regardless of the reason(s) for withdrawal. In addition, a patient may discontinue his or her participation at any time during the study without having to justify the decision. If a patient's participation is discontinued, the reason(s) must be recorded in the source documents and on the eCRF. If a patient discontinues for any reason, every effort should be made to perform all of the procedures that are scheduled for the End-of-Study/ Early Termination Visit. In addition, SAEs, related or not and ADEs, will be followed post-study according to the safety plan.

---

## 6.9 Other Study Procedures

- Comprehension and retention testing (materials provided by Baxter) for patient and/or care partner (if participating) will occur at the end of the Baseline Period (In-center Training Period). If the patient does not read and understand English, the care partner will assist the patient with comprehension and retention testing. The Investigator or a designee must also reassess the stability of the patient during the Baseline Period (In-center Training Period). Once the clinician concludes that the patient is clinically stable and his/her PD prescription is stable, then the patient can begin treatment in the home.
- Home installation will occur during the Screening or the Baseline Period (In-center Training Period).
- The patient will conduct chlorine testing prior to every treatment.
- Additional testing and procedures will be performed per local standard of care.

## 6.10 Appropriateness of Measurements

Measurements for the primary and secondary endpoints are well accepted. Other chemistry and hematology measurements to evaluate safety are standard for the indication or patient population being studied.

## 7. DATA COLLECTION FOR SAFETY ASSESSMENTS AND REPORTING

### 7.1 Definition of Adverse Events and Device Deficiencies

**Table 5. Adverse Event Term Definition**

Term	Definition
Adverse Event (AE)	Any untoward medical occurrence in a patient or clinical investigation subject administered a product which does not necessarily have a causal relationship with this treatment.
Adverse Drug Reaction (ADR) or Adverse Reaction (AR) /Adverse Device Effect (ADE)	Adverse event related to the use of study product.
Suspected Adverse Reaction (SAR)	Any AE for which there is a reasonable possibility that the product caused the AE. For the purposes of IND safety reporting “reasonable possibility” means there is evidence to suggest a causal relationship between the product and the AE.
Unexpected Adverse Drug Reaction (UADR)	An adverse reaction in which the nature or severity is not consistent with the applicable product information (e.g., Investigator’s Brochure for unapproved

**Table 5. Adverse Event Term Definition**

Term	Definition
	
investigational product or package insert/summary of product characteristics for an approved product). (ICH E6 (R2))
 
The Adverse reaction may not be listed at the specificity or severity that has been observed; or if an investigator brochure is not required or available, is not consistent with the risk information described in the general investigational plan or elsewhere in the current application, as amended. (21 CFR 312.32)

Adverse Event of Special Interest (AESI)
	
An adverse event of special interest (serious or non-serious) is one of scientific and medical concern specific to the Sponsor’s product or program, for which ongoing monitoring and rapid communication by the investigator to the Sponsor can be appropriate. Such an event might warrant further investigation in order to characterize and understand it. Depending on the nature of the event, rapid communication by the study Sponsor to other parties (e.g., regulators) might also be warranted. (FDA Guidance for Industry E2F).

Serious Adverse Event (SAE) or Serious Adverse Drug Reaction (SADR) or Serious Adverse Device Effect (SADE)
	
Any untoward medical occurrence that at any dose:
 
 
• Results in death (including fetal death).
 
• Is life-threatening.
 
• Requires inpatient hospitalization or results in prolongation of existing hospitalization.
 
• Results in persistent or significant disability/incapacity.
 
• Is a congenital anomaly/birth defect (ICH E6 (R2)).
 
• Is a medically important event or reaction that may not be immediately life-threatening or result in death or hospitalization, but may jeopardize the patient or requires intervention to prevent one of the other outcomes listed above.
 

Device Deficiency (DD)
	
Inadequacy of an (investigational) medical device related to its identity, quality, durability, reliability, safety or performance, such as malfunction, misuse or use error and inadequate labeling.
 
This includes DDs that might have led to an SAE if:
 
 
• Suitable action had not been taken or
 
• Intervention had not been made or
 
• If circumstances had been less fortunate.
 


Suspected Unexpected Serious Adverse Reaction (SUSAR) /Unanticipated Adverse Device Effect (UADE)
	
An AE that in the view of the Investigator or Sponsor, meets the definition of serious, unexpected, and is suspected to have a causal relationship to study product. Suspected Unexpected Serious Adverse Reactions are also reportable for active comparator products, placebo, or the clinical study protocol itself (i.e., events due to study procedures).
 
Any SADE on health or safety or any life-threatening problem or death caused by, or associated with, a device, if that effect, problem, or death was not previously identified in nature, severity, or degree of incidence in the investigational plan or application (including a supplementary plan or application), or any other unanticipated serious problem associated with a device that relates to the rights, safety, or welfare of patients.

**Table 6. Definition of Terms**

Term	Definition
Awareness Date or Baxter Awareness Date (BAD)	The date on which any Baxter employee or their agent becomes aware of an adverse event (AE). This date is considered Day 0 on the regulatory reporting time clock.
Date of Onset	The date when the signs and symptoms of the AE begin.
Investigational Product (IP)	Experimental product under study or development. This term is more specific than investigational medicinal product, which includes comparators and placebos. For this protocol, the term “investigational drug” is synonymous with “investigational product”. For this protocol, the term “investigational product” is synonymous with AMIA APD Solution Generation System.
Diagnosis vs Complications	A patient experiences not only a diagnosis, but also additionally a complication of the diagnosis (i.e., myocardial infarction with congestive heart failure); both the diagnosis and the medical complication should be collected and recorded as separate AEs.

## 7.2 Safety Reporting

All AEs, PCs and DDs observed by the study personnel or reported by the patient during the course of the study will be documented from the time of signing the ICF through the End-of-Study/ Early Termination Visit.

Any medical condition, that is present at the time that the participant is screened, will be considered medical history and not reported as an AE (see [Appendix 6](#)). Any medical event that is commonly associated with a study participant’s PD therapy will be considered medical history and not reported as an AE (see [Appendix 6](#)). However, if the study patient’s condition/event worsens (change in severity or frequency) at any time during the study, it will be recorded as an AE.

If a definitive diagnosis has been medically established by the physician caring for the patient or by the Investigator, this diagnosis should then be recorded as the AE on the eCRF and the signs and symptoms removed. If a definitive diagnosis has not been medically established, the signs and symptoms should then be recorded as the AEs.

Adverse events that change in severity will be reported at each incidence, but documented only once in the eCRF with the highest degree of severity.

An elective procedure/ surgery that occurs during the course of a study, but is being performed for a documented pre-existing condition and was pre-planned prior to study entry will not qualify as an AE. If, however, the pre-existing condition unexpectedly deteriorates during the study requiring the procedure/ surgery to be performed earlier than planned, the condition for which the procedure/ surgery is being performed will qualify as an AE.

Laboratory and vital sign abnormalities qualify as AEs if medical intervention is required to treat or address the abnormality, if the patient must be discontinued from the study due to the abnormality, or if the Investigator determines the value is clinically significant.

An AE can result from the use of the study product in accordance with the protocol, as well as from an accidental or intentional misuse of the study product or any other treatment error such as unintentional administration or use of another product during the course of the study.

If an AE or DD occurs, a full description of the event should be recorded including the date and time of onset, as well as outcome, seriousness, severity, event description, actions taken, and causal relationship of the AE. Investigators should review and reference the causality (see [Table 7](#)) and severity definitions (see [Table 8](#)) when determining relationship of the AE to the study product or typical PD therapy. The Investigators may also discuss the event(s) with the Baxter Medical Monitor or designee.

All AEs should be actively solicited and documented in the eCRFs, no matter how common they are for a particular patient and regardless of the causality assigned by the Investigator. Additionally, any AE voluntarily reported by the patient should be recorded and verified by the Investigator or a designee with the relevant source documents and eCRF. Each SAE will be documented on a separate SAE report form.

The outcome/ resolution of all AEs will be determined by the Investigator and documented in the AE eCRF. Investigators will be instructed to follow all treatment emergent AEs as follows: Adverse device effects (related AEs) and all SAEs (related or not) will be followed until resolution or stable, including following the patient after the end of the study if necessary.

For the outcome conclusions that can be used on the eCRF by the Investigator, refer to [Table 9](#).

---

If a patient in this study also receives a Baxter medicinal/ drug product which is part of a patient's normal treatment (not an investigational product or comparator), any AE which is considered causally related to the medicinal/ drug product by either the Investigator or the medical monitor shall be forwarded by the Investigator or a designee within 24 hours of becoming aware of the AE to Baxter Global Patient Safety

( [REDACTED] ) for assessment as per Baxter's process for case processing of spontaneous reports.

Causality is a determination of whether there is a reasonable possibility that the study product is etiologically related to/ associated with an AE. Causality assessment includes, for example, assessment of temporal relationships, dechallenge/rechallenge information, association (or lack thereof) with underlying disease, presence (or absence) of a more likely cause, and physiologic plausibility.

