### **7.2.2 Medical Events Commonly Associated with Peritoneal Dialysis**

The medical events and their definitions, that have been commonly reported as possibly related to PD therapy in general, are provided in [Appendix 6](#). This list has been provided to ensure these events are captured in the patients' medical history, when appropriate. If an event is part of the patient's medical history, it will not be considered as an AE for the study unless the frequency increases or the severity worsens.

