## Appendix 6 Medical Events Commonly Associated with Peritoneal Dialysis

The following are medical events that have been commonly reported as possibly related to PD therapy in general:

Abdominal pain:	A generic term for focal or general discomfort localized to the abdominal region.
Back pain:	Pain felt in or along the spine or musculature of the posterior thorax.
Bleeding:	The escape of blood from an injured vessel.
Chest pain:	A general term for any dull, aching pain in the thorax, usually referring to that of acute onset, which is often regarded as being myocardial in origin unless proven otherwise.
Drain pain (outflow pain):	A sense of abdominal discomfort; pain or crampy discomfort arising during the drain phase of a peritoneal dialysis exchange that may occur during a manual or automated peritoneal dialysis exchanges.
Edema (Peripheral and/or facial; Scrotal):	An abnormal accumulation of fluid in intercellular spaces of the body.
Fever:	A fever is any body temperature elevation over 100 °F (37.8 °C).
Headache:	Pain in the head which can arise from many disorders or may be a disorder in and of itself.
Hematuria:	Presence of blood or red blood cells in the urine.
Hernia:	Protrusion of a part or structure through the tissues normally containing it.
Hydrothorax:	Accumulation of serous fluid in one or both pleural cavities.
Hypertension:	Persistently high arterial blood pressure.
Hypoglycemia:	An abnormally low level of glucose in the blood.
Hypotension:	Persistently low arterial blood pressure.
Itching:	An uncomfortable sensation of irritation of the skin or mucous membranes that causes scratching or rubbing of the affected parts.
Chills:	A sensation of cold, with convulsive shaking of the body.
Muscle cramps:	A sudden and involuntary contraction of one or more muscles
Nausea:	An unpleasant sensation vaguely referred to the epigastrium and abdomen, with a tendency to vomit.
PD catheter leak:	An appearance of any moisture around the PD catheter identified as dialysate.
Vomiting:	The ejection of matter from the stomach in retrograde fashion through the esophagus and mouth.

---

This list does not include medical events that are part of the exclusion criteria and/or should always be considered an AE regardless of medical history, severity or frequency.

---

---

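### Protocol 7.2 can be read to keep first occurrences of common PD events out of the adverse event data, in conflict with 7.2.2 and 7.2.3

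*Protocol*

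**What the plan says.** Protocol 7.2 removes two kinds of event from AE reporting, in consecutive sentences that both cite Appendix 6. The first covers any medical condition "that is present at the time that the participant is screened, will be considered medical history". The second covers any medical event commonly associated with a study participant's "PD therapy will be considered medical history and not reported as an AE". The sentence after these brings some events back: if the patient's "condition/event worsens (change in severity or frequency) at any time during the study, it will be recorded as an AE".

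Appendix 6 introduces its list with "The following are medical events that have been commonly reported as possibly related to PD therapy in general". The list has 20 terms, among them abdominal pain, chest pain, bleeding, fever, chills, hypotension, hernia, hydrothorax and PD catheter leak.

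Other places bear on the same question:

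- Protocol 7.2.2 limits its exclusion to events in the patient's own medical history; of such an event it says "it will not be considered as an AE for the study unless the frequency increases or the severity worsens". Protocol 7.2.3 repeats this among the investigator's reporting duties.
- A later paragraph of Protocol 7.2 says "All AEs should be actively solicited and documented in the eCRFs, no matter how common they are for a particular patient".
- Protocol 7.2 also says "Laboratory and vital sign abnormalities qualify as AEs if medical intervention is required to treat or address the abnormality", or if the abnormality leads to discontinuation or the investigator judges it clinically significant.
- SAP 16.1 carries over only the present-at-screening rule.
- Protocol 10.6 and SAP 14.2.4 plan summaries of AEs by relationship to typical PD therapy.

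**The concern.** The first exclusion already deals with what the patient brings into the study. If the second meant only pre-existing events, it would add little. Its plain wording reaches further, to events that are common on PD, whether or not this patient has had them before.

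AEs, SAEs, ADEs and SADEs form a secondary endpoint (Protocol 3.2.2). An event filed as medical history has no AE record. Protocol Table 5 defines an ADE as an AE related to the study product, so such an event may also never be assessed for causality. The SAP's treatment-emergent counts, patient-year rates, PD-related tables and table of AEs in at least 5% of patients all depend on this first classification. The study has one arm and up to 15 sites. Under-recording would not cancel against a control group, and sites that read the section differently would contribute data that are not comparable.

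**Working it through.** No formula applies to the main question, and the plan states no figure to reproduce. The check is to put one case through each passage: a patient with no history of abdominal pain reports it for the first time during the Study Treatment Period, and no diagnosis is made.

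| Place | Rule as worded | Result for this case |
|---|---|---|
| 7.2, first exclusion | Condition present when screened | Not excluded |
| 7.2, second exclusion with Appendix 6 | Event commonly associated with the participant's PD therapy | Excluded on a literal reading |
| 7.2, worsening clause | Change in severity or frequency | Unclear: no earlier state to worsen |
| 7.2, undiagnosed events | Signs and symptoms recorded as AEs | Recorded |
| 7.2, later paragraph | All AEs documented however common | Recorded, if the event counts as an AE at all |
| 7.2.2 and 7.2.3 | Excluded only if in the patient's own history and not worse | Recorded |
| SAP 16.1 | Present-at-screening rule only | Recorded |

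**Scope of the list.** Appendix 6 describes PD in general, not one patient's history. By contrast, 7.2.2 says the list exists so that such events reach the medical history when appropriate. That is a prompt for history taking, not a class exemption.

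**Reach of the vital-sign and laboratory rule.** Of the 20 terms, it plausibly reaches fever, hypertension and hypotension (vital signs) and hypoglycemia (laboratory), provided one of its three conditions is met. It does not help with abdominal pain, chest pain, bleeding, hydrothorax or catheter leak.

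**Planned tables.** SAP 14.2.4 calls for treatment-emergent AEs related to typical PD therapy. Under the literal reading these would hold mainly worsened events and PD-related events not on the list. The tables make better sense if first occurrences are recorded.

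**A further sign of loose drafting.** The closing note to Appendix 6 says the list omits events that are part of the exclusion criteria. Hernia is listed, yet current abdominal hernia is exclusion criterion 10. An abdominal hernia arising in the study would normally be new or recurrent.

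**Leverage of one classification.** This shows how few patients matter; it does not estimate bias. Assume a Safety Set between the 30-completer target and the enrollment cap of 50. With 30 patients, 1/30 = 3.3% and 2/30 = 6.7%. With 50 patients, 2/50 = 4.0% and 3/50 = 6.0%. At either size, one patient classified differently can move a preferred term into or out of the 5% table.

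**The case against.** The strongest reply is that the intended rule is clear from the rest of the plan. The disputed sentence speaks of a study participant's PD therapy, which allows a patient-specific reading. Sections 7.2.2 and 7.2.3 state the narrower rule outright, and the SAP is consistent with it. The worsening clause covers events as well as conditions and glosses worsening as a change in severity or frequency, so going from none to one could count. The vital-sign rule catches some fever and hypotension. All of this stands. It shows that the sentence is ambiguous and that a careful site could reach the right answer. It does not show that every site would, because the Appendix 6 reference points the other way and nothing in 7.2 mentions a first occurrence.

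It can also be said that the instruction to document all AEs does not contradict the exclusion, since one defines what an AE is and the other says to record it. That is a fair reading. However, the words about how common an event is for a particular patient also sit awkwardly with 7.2.2, which sets aside events already usual for that patient. Correcting the exclusion alone would leave that tension.

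A reader might go further and infer that the main signals of contaminated or wrongly mixed solution would be lost. The documents do not support that. None of the nine AESIs in Protocol 7.2.1, which include aseptic peritonitis and administration of an incorrect glucose concentration, is on the Appendix 6 list. Contamination and composition are also tested directly as primary endpoints.

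**Conclusion.** The inconsistency is real and worth correcting. One sentence in Protocol 7.2, followed literally, excludes first occurrences of the 20 Appendix 6 events or leaves their exclusion open, whereas 7.2.2 and 7.2.3 would have them recorded. The likely direction of error is an undercount of the AE secondary endpoint, with differences between sites.

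A reader might infer that the protocol flatly suppresses all new-onset PD-type events, or might attach a percentage to the loss. Neither follows. The first ignores the patient-specific wording, the worsening clause and the vital-sign rule. The second needs the share of AEs falling under Appendix 6 terms and the number of sites applying the literal reading, and the documents give neither. The conclusion rests on the wording alone and assumes that some sites would follow the second exclusion as written.

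**What to change.** Replace the second exclusion sentence in Protocol 7.2 with the rule already in 7.2.2 and 7.2.3. Suggested text: *An Appendix 6 event is not an AE only if it is already documented in that patient's medical history at screening and has not since increased in frequency or severity. A first occurrence after that point is recorded as an AE.* The screening cutoff matches the adjacent sentence in 7.2 and SAP 16.1. Consent is signed on the first day of a Screening Period of about three weeks and AE collection starts then, so the site instruction should say which day of screening fixes the history.

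Amend the later sentence in 7.2 on soliciting and documenting all AEs to say that it applies to events that qualify as AEs under this rule. Tell sites by memo and in training.

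The cost is two sentences in an amendment and one memo. More AEs will be recorded, which is the purpose of the change. It concerns recording only and alters no clinical management.
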